1. INTRODUCTION

The purpose of this reporting and analysis plan (RAP) is to describe the analyses to be included in the Clinical Study Report for Protocol:

Revision Chronology:		
GlaxoSmithKline Document Number	Date	Version
2016N277425_00	2016-SEP-13	Original
2016N277425_01	2017-FEB-07	Amendment No. 1

This protocol amendment was created to make the following changes:
 
Regulatory Agency Identifying Number(s): A typographical error in the EudraCT no. corrected. IND no. added
 
Section 4.1 and Section 4.4: Typographical errors and inconsistencies corrected
 
Inconsistencies between Section 4.4, Section 7.3.1.5 and Section 7.1 revised
 
Section 7.1 Time and Events table: Un-intentional deletion of the (“x”) were added to confirm that concomitant medications should be reviewed at every clinic visit was corrected. Increased the visit window Typographical error and inconsistencies corrected as described in Appendix 9, Section 12.9.
 
Section 7.2.2 Critical procedures performed at Screening (Visit 1): To clarify that height and weight are collected at V1 “Height and weight” added
 
Section 7.3.2 Spirometry: “At Screening, before the morning dose of usual COPD medication(s)” added.
 
Section 7.3.7: Physical activity monitor (study subset) Inconsistency between Section 1, Section 4.1 and Section 7.3.7 revised
		
2016N277425_02	2017-FEB-21	Amendment No. 2 Canada ONLY

This protocol amendment was created to comply with Health Canada guidelines. They require pharmaceutical manufacturers to expeditiously report domestic cases of unusual failure in efficacy (UFIE) for new drugs to the Marketed Health Products Directorate (MHPD) within 15 days of first notification.
 
Changes were made to Section 7.4.1 and Appendix 4.
		

Revision Chronology:		
GlaxoSmithKline Document Number	Date	Version
2016N277425_03	2017-APR-18	Amendment No. 3
This protocol amendment was created to make the following changes: 
• Clarifications concerning study design, stratification, permitted and prohibited COPD medications, stopping criteria, visit windows, chest x-rays performed in the context of the protocol and site professional expertise• Rate of COPD exacerbations from tertiary endpoints to exploratory endpoints• Addition of an inclusion criterion specific to France• Integration of Canadian Amendment 2• Correction of typographical errors and inconsistencies		

Note there is a separate RAP to cover the required analyses for the German Federal Joint Committee (G-BA).

2. SUMMARY OF KEY PROTOCOL INFORMATION

2.1. Changes to the Protocol Defined Statistical Analysis Plan

Changes from the originally planned statistical analysis specified in the protocol are outlined in [Table 1](#).

Table 1 Changes to Protocol Defined Analysis Plan

Protocol	Reporting & Analysis Plan	
Statistical Analysis Plan	Statistical Analysis Plan	Rationale for Changes
	
 An additional population has been defined, the Activity Monitoring (AM) Population, which will comprise all subjects in the ITT population who provide data from at least one activity monitoring session. 	
 Population needed for subset of subjects participating in Activity Monitoring.
	
 All other Endpoints promoted to secondary endpoints 	
 Study aims have developed since protocol and thus previous endpoints classed as 'other' have further importance
	
 An analysis by Maintenance Naive (MN) and Non-Maintenance Naive subgroups have been included. 	
 To investigate prospectively the 1st line use of LAMA/LABA in all symptomatic subjects (no existing data the literature to our knowledge)
	
 An analysis of ratio of trough FEV1 to baseline trough FEV1 	
 To investigate trough FEV1 ratio change from baseline

 Intent-to-treat ICS free (ITT ICS free) 	
 Population excluded. 	
 G-BA analysis to be conducted on the ITT population due to a change in G-BA guidance.

 To compare albuterol/salbutamol use captured in the eDiary with the electronic metered dose inhaler (eMDI) Device as data allow 	
 Not included in this RAP. 	
 Will be included in a supplementary RAP if deemed necessary.

Protocol	Reporting & Analysis Plan	
Statistical Analysis Plan	Statistical Analysis Plan	Rationale for Changes

 To compare physical activity levels, ER-S, rescue medication use, hospital exacerbations and mortality in subjects with and without a CID 	
 To compare ER-S, rescue medication use, hospital exacerbations and mortality in subjects with and without a CID 	
 Physical activity levels will not be assessed via CID due to a smaller subset of subjects.

There were changes to the originally planned populations specified in the protocol (Dated: 13-SEP-2016) and [Table 1](#).

[figure not shown]
2.2. Study Objectives and Endpoints

Objectives	Endpoints
Primary	Primary

 To compare the effect of UMEC/VI (62.5/25 mcg once daily) with UMEC (62.5 mcg once daily) on lung function 	
 Change from baseline in trough Forced Expiratory Volume in One Second (FEV₁) at week 24
Secondary	Secondary

 To compare UMEC/VI (62.5/25 mcg once daily), UMEC (62.5 mcg once daily) with salmeterol (50 mcg twice daily) on patient reported outcomes (PROs) 	
 Change from baseline in self administered computerised (SAC) transient dyspnea index (TDI) Percentage of TDI responders according to SAC TDI score. A responder is defined as a ≥ 1 unit improvement in SAC TDI score Assessment of respiratory daily symptoms over 24 weeks using Evaluating Respiratory Symptoms- COPD (E-RS) and its subscales (breathlessness, cough and sputum and chest symptoms) Percentage of E-RS responders according to E-RS score (defined as reduction in E-RS score of ≥ 2 or ≥ 3.35 units) from baseline Change from baseline in St George's Respiratory Questionnaire (SGRQ-C) Percentage of responders according to SGRQ-C total score (defined as a 4 point or greater reduction from baseline) Change from baseline in COPD assessment test (CAT) Percentage of responders according to CAT

Objectives	Endpoints
	(defined as a ≥ 2 unit improvement in score from baseline)

 To compare UMEC/VI (62.5/25 mcg once daily), UMEC (62.5 mcg once daily) with salmeterol (50 mcg twice daily) on other COPD efficacy measures 	
 Ratio to baseline of trough Forced Expiratory Volume in One Second (FEV₁) Time to first mild, moderate or severe exacerbation Time to first moderate or severe exacerbation Time to first severe exacerbations Time to first clinically important deterioration (CID) composite endpoint Time to first clinically important deterioration composite endpoint excluding FEV₁ (Exacerbation, SGRQ, TDI, CAT) Rescue albuterol/salbutamol use, (percentage of rescue-free days and mean number of Inhalations/day) captured by the electronic diary (eDiary) over 24 weeks Inspiratory capacity (IC) Forced Vital capacity (FVC) Change from baseline in trough FEV₁ Change from baseline in global impression of disease severity

Objectives	Endpoints
Safety	Safety

 To evaluate safety and tolerability of UMEC/VI (62.5/25 mcg once daily), UMEC (62.5mcg once daily) and salmeterol 50mcg twice daily) 	
 Incidence of adverse events
Exploratory	Exploratory

 To explore the effect of UMEC/VI (62.5/25 mcg once daily), UMEC (62.5 mcg once daily) with salmeterol (50 mcg twice daily) on rate of COPD exacerbation 	
 Rate of mild, moderate or severe exacerbations Rate of moderate or severe exacerbation

 To explore the effect of UMEC/VI (62.5/25 mcg once daily), UMEC (62.5 mcg once daily) with salmeterol (50 mcg twice daily) on physical activity 	
 Change from baseline in physical activity

 To investigate the CID composite endpoint ability to predict short term outcomes 	
 To compare ER-S, rescue medication use, hospital exacerbations and mortality in subjects with and without a CID

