2.4. Statistical Hypotheses

The primary purpose of this study is to demonstrate improvements in lung function for subjects treated with UMEC/VI compared with UMEC for 24 weeks.

The primary endpoint is change from baseline in trough FEV₁ at Week 24.

The null hypothesis is no difference between treatment groups ($H_0: \mu_T - \mu_S = 0$), with the alternative hypothesis that there is a difference between treatment groups ($H_1: \mu_T - \mu_S \neq 0$), where μ_T is the mean change from baseline for UMEC/VI and μ_S is the mean change from baseline for UMEC.

In order to account for multiplicity across treatment comparisons and endpoints, a step-down closed testing procedure will be applied whereby inference for secondary endpoints or treatment comparisons are dependent upon statistical significance having been achieved for the primary comparison. If the primary comparison is significant i.e. the associated p-value for UMEC/VI versus UMEC for change from baseline in trough FEV₁ at Week 24 is below 0.05, this will allow inference of treatment comparisons (UMEC/VI versus UMEC on all secondary endpoints, and UMEC/VI versus Salmeterol and UMEC versus Salmeterol on all primary and secondary endpoints), which will be declared statistically significant if the associated p-value is below 0.05.

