- Least squares (LS) mean and LS mean changes from baseline with their corresponding standard errors (SEs) will be presented for each treatment by visit, together with estimated treatment differences (UMEC/VI 62.5/25 vs. UMEC 62.5, UMEC/VI 62.5/25 vs Salmeterol and UMEC 62.5 vs Salmeterol), corresponding 95% CIs and p-values.
- A plot of LS mean changes from baseline and 95% CIs for each treatment by visit will be generated.
- A plot of LS mean treatment differences and 95% CIs between the treatment groups by visit will also be generated.
- The type III tests of fixed effects and the covariance parameter estimates from the model will be presented in two tables.

Summary Results Presentation

- Summary of baseline FEV₁ will be presented by treatment for all subjects.
- A box plot and an empirical distribution function plot of change from baseline in trough FEV₁ at Week 24 will be produced.
- Summary statistics for raw and change from baseline in trough FEV₁ at each visit and for each treatment will be presented on the same table.

Sensitivity and Support Statistical Analysis

- An assessment of whether the effect of treatment is modified by the interaction with
 - o Baseline FEV₁
 - o Geographical Region
 - o Stratum (no. of bronchodilators per day during run-in)
 will be made (for primary endpoint only for the ITT population only) by fitting separate MMRM models including an additional term for treatment by each covariate. The interaction term will be tested at the 10% significance level.
- For factors with two levels or continuous factors i.e. Baseline FEV₁ and Stratum, interactions with treatment will be investigated by fitting a model with the same terms as the main model, and adding in treatment by factor by Visit interaction. Contrast statements will be used to obtain the p-value for the treatment by factor interaction at Week 24. If that p-value is ≥ 0.10 the interaction will be considered not significant. If the p-value is < 0.10 , further investigation will be performed, for example running analysis by each level of the factor, or for subgroups

above and below the median.

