7.2.2. Summary Measure

- 1) Mean change from BDI score
- 2) Mean change from baseline
- 3) Mean change from baseline
- 4) Mean change from baseline
- 5) Odds ratio
- 6) Odds ratio
- 7) Odds ratio
- 8) Odds ratio
- 9) Hazard ratio
- 10) Hazard ratio
- 11) Hazard ratio
- 12) Hazard ratio
- 13) Hazard ratio
- 14) Mean change from baseline
- 15) Mean change from baseline
- 16) Ratio of trough FEV1 to baseline FEV1
- 17) Mean change from baseline
- 18) Mean change from baseline
- 19) Odds ratio

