7.2.5.1. Statistical Methodology Specification

TDI, E-RS, SGRQ-C and CAT Scores

Secondary Statistical Analysis
Endpoints

 • SAC TDI focal score • Assessment of respiratory daily symptoms using E-RS and its subscales • Change from baseline in SGRQ • Change from baseline in CAT
Model Specification, Checking and Results Presentation

 • Similar to trough FEV1 in Section 7.1.5.1. • For TDI one model will be fitted with a dependent variable of TDI and BDI in place of baseline. • For E-RS and subscales, all 4-weekly mean scores will be included in the analysis.

Responders according to TDI, E-RS, SGRQ-C and CAT Scores

Secondary Statistical Analysis
Endpoints

 • Proportion of responders according to TDI focal score • Proportion of responders according to E-RS total score • Proportion of responders according to E-RS Breathlessness score • Proportion of responders according to E-RS Cough & Sputum score • Proportion of responders according to E-RS Chest Symptoms score • Proportion of responders according to SGRQ total score • Proportion of responders according to CAT score
Model Specification

 • The proportion of responders will be analyzed using a generalized linear mixed model with treatment as an explanatory variable and visit, baseline score, stratum (no. of bronchodilators per day during run-in), geographical region, visit by baseline score and visit by treatment interactions included as covariates. • Model using proc glimmix with; random visit / subject=subject*period residual type=un statement to account for repeated visit; • For TDI the model will use BDI in place of baseline score. • For E-RS the model will use 4 weekly period in place of visit. • This analysis will include all subjects with a non-missing baseline assessment. See Section 10.6.2.3 for details on how to handle missing data.
Model Checking & Diagnostics

 • UMEC will be used as the reference level for treatment for the comparison between UMEC/VI vs. UMEC. Salmeterol will be used as the reference level for treatment for the comparison between UMEC/VI vs. Salmeterol and UMEC vs Salmeterol.

Secondary Statistical Analysis

 Pearson residuals will be plotted by using PLOTS=RESIDUALPANEL option for the model statement in SAS.
Model Results Presentation

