
 Similar to trough FEV1 in Section 7.1.5.1 where Visit is replaced with 4-weekly period. The model will use all available values: 
 Periods defined as Weeks 1-4, 5-8, 9-12, and up to Weeks 21-24 Baseline is defined in Section 5.2 Model will include the period by baseline and period by treatment interaction. Overall treatment effect from the same model using overall main effect on Lsmean statement.
Sensitivity and Supportive Statistical Analyses

 If the assumption of normality for the percentage of rescue-free days is not satisfied, a non-

Secondary Statistical Analysis
parametric analysis of percentage of rescue-free days will be carried out. Hodges Lehman estimates for the median treatment difference and 95% CI based upon a Wilcoxon rank sum test will be used. The p-value will be based on Van Elteren test, an extension to the Wilcoxon rank sum test for two group comparison, stratified by geographical region.

Trough FEV1, FVC and IC

Secondary Statistical Analysis
Endpoints

 • Ratio of trough FEV1 to baseline FEV1 • Trough FVC • Trough IC
Model Specification

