10.8.4. Efficacy Tables

Efficacy: Tables				
No.	Population	Title	Programming Note	Deliverable
2.01	ITT	Summary of Baseline FEV1 (L)		SAC
2.02	ITT	Summary of Trough FEV1 (L)		SAC
2.03	ITT	Analysis of Trough FEV1 (L)		SAC
2.04	ITT	Covariance Parameter Estimates for Repeated Measures Analysis of Trough FEV1 (L)		SAC
2.05	ITT	Type III Tests of Fixed Effects for Repeated Measures Analysis of Trough FEV1 (L)		SAC
2.06	ITT	Significance Levels for Interactions of Treatment with Baseline FEV1, Geographical Region and Stratum for Trough FEV1 (L)		SAC
2.07	ITT	Analysis of Ratio (Trough FEV1/Baseline FEV1)		SAC
2.08	ITT	Summary of Baseline FVC (L)		SAC
2.09	ITT	Summary of Trough FVC (L)		SAC
2.10	ITT	Analysis of Trough FVC (L)		SAC
2.11	ITT	Summary of Baseline IC (L)		SAC
2.12	ITT	Summary of Trough IC (L)		SAC
2.13	ITT	Analysis of Trough IC (L)		SAC
BDI/TDI				
2.14	ITT	Summary of BDI Focal Score		SAC
2.15	ITT	Summary of TDI Focal Score		SAC
2.16	ITT	Analysis of TDI Focal Score		SAC
2.17	ITT	Summary and Analysis of Proportion of Responders According to TDI Focal Score		SAC
E-RS				
2.18	ITT	Summary of Four-Weekly Mean E-RS Total Score		SAC
2.19	ITT	Summary of Four-Weekly Mean E-RS Breathlessness Score		SAC

Efficacy: Tables				
No.	Population	Title	Programming Note	Deliverable
2.20	ITT	Summary of Four-Weekly Mean E-RS Cough and Sputum Score		SAC
2.21	ITT	Summary of Four-Weekly Mean E-RS Chest Score		SAC
2.22	ITT	Analysis of Four-Weekly Mean E-RS Total Score		SAC
2.23	ITT	Analysis of Four-Weekly Mean E-RS Breathlessness Score		SAC
2.24	ITT	Analysis of Four-Weekly Mean E-RS Cough and Sputum Score		SAC
2.25	ITT	Analysis of Four-Weekly Mean E-RS Chest Score		SAC
2.26	ITT	Summary and Analysis of Proportion of Responders According To E-RS Total Score		SAC
2.27	ITT	Summary and Analysis of Proportion of Responders According To E-RS Breathlessness Score		SAC
2.28	ITT	Summary and Analysis of Proportion of Responders According To E-RS Cough and Sputum Score		SAC
2.29	ITT	Summary and Analysis of Proportion of Responders According To E-RS Chest Score		SAC
SGRQ-C				
2.30	ITT	Summary of Baseline SGRQ Scores		SAC
2.31	ITT	Summary of SGRQ Total Score		SAC
2.32	ITT	Summary of SGRQ Symptoms Score		SAC
2.33	ITT	Summary of SGRQ Activity Score		SAC
2.34	ITT	Summary of SGRQ Impacts Score		SAC
2.35	ITT	Analysis of SGRQ Total Score		SAC
2.36	ITT	Summary and Analysis of Proportion of Responders According To SGRQ Total Score		SAC
CAT				
2.37	ITT	Summary of CAT Score	Include Baseline	SAC

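### E-RS is declared over 24 weeks but is analysed only as six 4-weekly contrasts, none named as the one that decides the claim

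*SAP*

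**What the plan says.** SAP Section 2.2 declares the endpoint as "Assessment of respiratory daily symptoms over 24 weeks using Evaluating Respiratory Symptoms- COPD (E-RS) and its subscales". In the same table, eDiary rescue use is also declared over 24 weeks. Section 7.2.2 gives the E-RS summary measure as "2) Mean change from baseline", with no time point and no averaging period.

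Section 7.2.5.1 specifies the E-RS analysis as "Similar to trough FEV1 in Section 7.1.5.1" and adds that "For E-RS and subscales, all 4-weekly mean scores will be included in the analysis". In the trough FEV1 template, the results "will be presented for each treatment by visit, together with estimated treatment differences", confidence intervals and p-values. For E-RS the repeated factor is the 4-weekly period, so the output is by period. Section 10.5.3 derives E-RS and its subscales only as means within the 4-weekly intervals. Table 2.22 is titled "Analysis of Four-Weekly Mean E-RS Total Score". Tables 2.23-2.25, Figures 2.11-2.18 and the maintenance-naive subgroup Table 2.93 follow the same pattern.

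For rescue use, Section 7.2.5.1 uses the same model type and the same six periods, but it also states: "Overall treatment effect from the same model using overall main effect on Lsmean statement". Tables 2.61 and 2.63 are titled for Weeks 1-24.

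Under Section 2.4, once the primary comparison succeeds, inference extends to the comparisons on all secondary endpoints, "which will be declared statistically significant if the associated p-value is below 0.05".

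**The concern.** The rule in Section 2.4 needs one p-value for each endpoint and treatment comparison. For E-RS the plan supplies six and does not say which one counts. The deciding time point of trough FEV1, Week 24, is fixed for that endpoint only. Borrowing it for E-RS would mean Weeks 21-24, which fits poorly with an endpoint described over 24 weeks.

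The rescue-use specification shows that the plan's authors had a ready way to turn a 24-week diary endpoint into a single result, and that they did not apply it to E-RS. Without it, the choice of period, or of how many periods must agree, could be made after the results are known. A significance claim for the total score or any of the three subscales would then rest on a rule that was never written down.

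This differs from the absence of adjustment across secondary endpoints. Even with full adjustment across endpoints, one p-value per endpoint would still have to be named.

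**Working it through.** The plan states no power, sample size or error rate for E-RS, so there is no figure of its own to reproduce.

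**Inputs from the SAP**
- Treatment period for diary data: Days 1-168, in 28-day periods (Section 10.5.3).
- Treatment comparisons: 3 (Section 7.1.5.1).
- E-RS scores: total plus 3 subscales = 4 (Section 2.2).
- Significance level: 0.05 for each secondary comparison (Section 2.4).

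**Input assumed**
- Correlation between the period contrasts. The SAP gives none, so a range is shown.

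**Step 1: count the contrasts**
- Periods: 168 / 28 = 6.
- Contrasts per score: 6 × 3 = 18. Over four scores: 18 × 4 = 72.
- With one overall contrast per comparison: 3 per score and 3 × 4 = 12 over four scores.

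**Step 2: type I error for one score and one comparison, under three possible rules**

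For six independent tests, the chance of at least one p<0.05 is 1 − 0.95^6 = 0.265. For correlated tests, six standard normal statistics with common correlation ρ were simulated (500,000 draws), counting |Z| > 1.96.

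| ρ (assumed) | One prespecified period | Any period | All six periods |
|---|---|---|---|
| 0.5 | 0.05 | 0.21 | 0.0006 |
| 0.7 | 0.05 | 0.16 | 0.003 |
| 0.8 | 0.05 | 0.14 | 0.007 |
| 0.9 | 0.05 | 0.11 | 0.015 |

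If correlation instead decays with the distance between periods (first-order autoregressive), the any-period figures are 0.20, 0.17 and 0.13 for adjacent correlations of 0.7, 0.8 and 0.9.

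**Step 3: how often the periods would disagree**

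Take a constant true effect with an expected Z of 2.0 to 2.5 in every period. The six results are then mixed (some above 1.96, some not) in about 55% of trials at ρ = 0.7 with Z = 2.0, falling to about 27% at ρ = 0.9 with Z = 2.5. The choice of rule would often change the conclusion.

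**Step 4: the overall contrast**

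The equally weighted mean of six period contrasts with equal variances and common correlation ρ has a standard error of √((1 + 5ρ)/6) times that of one period. This gives 0.76, 0.87, 0.91 and 0.96 at ρ = 0.5, 0.7, 0.8 and 0.9. Its simulated type I error was 0.049 to 0.050 at these correlations.

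**The case against.** The 24-week wording in Section 2.2 can be read as describing when symptoms are assessed, not as requiring one 24-week mean. The six periods cover Days 1-168 without a gap, and Sections 7.2.1 and 7.2.2 mention no average. A reader might therefore infer too much by saying that the declared endpoint is not estimated at all. The document does not go that far, and this part of the objection stands. What remains is that the same time frame is turned into an overall estimate for rescue use and not for E-RS.

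The fitted model contains a treatment main effect, and the diary table in Section 10.5.3 has a Weeks 1-24 row, so the overall contrast could be obtained without new data. That is true, but nothing tells the programmer to produce it for E-RS. The Type III table (Table 2.05) is listed for trough FEV1 only, and a main effect across three arms is a 2-degree-of-freedom test, not a pairwise comparison.

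A reader might also infer that the plan inflates the E-RS false-positive rate to between two and four times 0.05. That holds only if any one significant period may support the claim, and the SAP states no such rule. A stricter rule would push the rate far below 0.05.

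Finally, TDI, SGRQ, CAT, FVC and IC also lack a named deciding visit. That is correct. What is particular to E-RS is the conflict with its sister diary endpoint.

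**Conclusion.** The point holds as a gap in specification. E-RS total and subscales have six period contrasts per comparison, no named deciding contrast and no planned Weeks 1-24 estimate, while rescue use, from the same diary and the same periods, has both the estimate and the tables.

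The consequence is an undefined error rate, not a known inflation: 0.05, about 0.11 to 0.21, or 0.0006 to 0.015, depending on a rule the plan does not give. The last two ranges rest on assumed equal correlations between 0.5 and 0.9. The gain in precision from averaging also assumes equal variances, and it becomes a gain in power only if the effect is similar across periods. The gap itself does not depend on any of these assumptions.

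The endpoints are secondary but eligible for significance claims, so the plan should be corrected before unblinding.

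**What to change.** In Section 7.2.5.1, for E-RS total and each subscale:

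- Add the overall Weeks 1-24 treatment contrast from the same MMRM, as the equally weighted average of the six period LS-mean differences, matching what is already planned for rescue use.
- State that this contrast is the one to which the Section 2.4 rule applies, and label the six period contrasts descriptive.
- Add the overall row to Tables 2.22-2.25 and 2.93.
- Name one deciding contrast for the E-RS responder analyses (Tables 2.26-2.29 and 2.94), which are also run by 4-weekly period.

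Naming a single 4-weekly period as decisive and amending Section 2.2 to match would also close the gap. The overall contrast is preferable because it fits the stated time frame and the treatment of rescue use.

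For the continuous scores, the cost is SAP wording and one extra estimate statement in a model already planned. There are two downsides. A single significant 4-week period can no longer support a claim, and the overall average includes the early treatment weeks, so it is not an estimate of late-treatment effect.
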